Primary endpoints	
Efficacy
 
 
1. Change in <math>\text{PaO}_2/\text{FiO}_2</math> ratio from baseline(as defined in sections 7.1.2 and 7.1.3, daily during treatment, end of treatment and 3 and 5 days post treatment in the groups receiving rtPA)
 
 
Safety
 
 
1. Incidence and severity of major bleeding events directly attributable to the study drug
 
2. Decrease in fibrinogen levels to < 1.0 gm/L during treatment period and 48 hrs after the last dose of treatment
 
3. Number and nature of serious adverse events causally related to the treatment
 

Secondary objectives	
 
1. Investigate the impact on patient's clinical status over time using the WHO ordinal scale of clinical improvement.
 
2. Investigate the effect of nebulised rtPA on other respiratory markers (such as lung compliance) and organ dysfunction
 
3. Investigate the impact on in hospital mortality and resource utilisation
 
4.
 

Secondary endpoints	
 
1. Changes in lung compliance (defined as tidal volume / (peak inspiratory pressure – PEEP) ) from baseline (as defined in sections 7.1.2 and 7.1.3) and absolute values at day 5, day 7, end of treatment, 3 days post end of treatment and 5 days post end of treatment
 
2. Clinical status as assessed by a 7-point WHO ordinal scale at baseline (as defined in sections 7.1.2 and 7.1.3), daily up to 5 days post end of treatment and at day 28, discharge or death (whichever comes first)
 
3. Mean daily Sequential Organ Failure Assessment (SOFA) score at baseline (as defined in sections 7.1.2 and 7.1.3) and daily up to 5 days post end of treatment.
 
4. In follow up period, number of oxygenation free days, ventilator free days, intensive care stay, up to 28 days or death or discharge, whichever occurs first.
 
5. Incidence and number of days of new oxygen use, non-invasive ventilation or high flow oxygen devices in the first 28 days.
 
6. Incidence and number of days of new mechanical ventilation use during in the first 28 days
 
7. In hospital mortality
 

Exploratory objectives	Changes to coagulation and inflammatory markers concerning intervention and response to treatment.

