### 10.1.2 Safety

1. Incidence and severity of major bleeding events directly attributable to the study drug
2. Decrease in fibrinogen levels to  $< 1.0 \text{ gm/L}$  during treatment period and 48 hrs after the last dose of treatment
3. Number and nature of serious adverse events causally related to the treatment

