## 10.6 Statistical analysis plan

All analyses will be descriptive in nature and should be considered as hypothesis generating rather than providing firm conclusions.

Analysis of cohorts 1 and 2 will be undertaken separately.

All study data will be listed and all relevant data will be tabulated and summarised separately by cohort and by group (rtPA treated, historical controls), separately for the patients receiving IMV, and for other patients with mild ARDS requiring non-invasive oxygen support at enrolment, and overall only where appropriate, as follows:

Planned recruitment for Cohort 1:

Group 1: Patients with ARDS receiving IMV at enrolment treated with rtPA (n=6)

Group 2: Patients with ARDS requiring non-invasive support at enrolment treated with rtPA (n=6)

Group 3: Patients with ARDS receiving IMV - historical controls (n=12)

Group 4: Patients with ARDS requiring non-invasive support - historical controls (n=12)

Planned recruitment for Cohort 2:

A total of 30 patients will be recruited, with a minimum of 10 from each ventilation type.

Group 5: Patients with ARDS receiving IMV at enrolment treated with rtPA

Group 6: Patients with ARDS requiring non-invasive support at enrolment treated with rtPA

Data will be presented using standard descriptive statistics. Continuous variables will be summarised using number of observations, mean, and standard deviation, median, inter-quartile range, minimum, and maximum values. Categorical values will be summarised using number of observations and percentages.

A statistical analysis plan will be written and finalised prior to database lock. This plan will give a detailed description of all summaries and results that will be presented. Cohort 1 data will be locked separately from the cohort 2 data and a separate SAP will be produced for the analysis of the cohort 2 data.

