### **10.6.2 Primary outcome analysis**

The PaO2/FiO2 ratio measured over time will be described for each group. The change from baseline in the PaO2/FiO2 ratio will be summarised at each post baseline timepoint. Plots will be used, where appropriate, to show the PaO2/FiO2 summarised for patients over time.

PaO2/FiO2 will be a calculated field on the trial database derived from the fields for PaO2 and FiO2. For cohort 2 data will be extracted once a day coinciding with the worst PF ratio. As PF ratio is the primary endpoint, in addition to the worst PF ratio, up to a maximum of 6 data points spread across 24 hrs that represents patients clinical status will be extracted. Details of further data derivation and analyses will be described in the SAP.

All patient data will be used, regardless of any intercurrent events that may have occurred after enrolment:

- Data from patients recruited into the rtPA + SOC group will be summarised whether or not patients have received all planned doses of the IMP.
- Any change in requirement for oxygenation and ventilation support will be summarised and described
- Changes in PaO2/FiO2 ratio over time will be described and interpreted taking into consideration that a patient's condition may have changed and led to their ventilation type changed post enrolment. If data allows, additional descriptions of the PaO2/FiO2 ratio over time may be performed in each subgroup of patients experiencing such changes (e.g. IMV to NIV, or vice versa).

The incidence and severity of bleeding events will be summarised in each group, and the change in fibrinogen levels will also be summarised at each post-baseline timepoint.

For cohort 1, subject to the final sample size and data quality, outcomes will also be compared between the SOC only group and intervention (rtPA + SOC) group using appropriate regression methods to make adjustment for baseline characteristics. Appropriate data transformations required for model assumptions will be considered if necessary.

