Nebulised rt-PA for ARDS due to COVID-19 – The PACA trial

Statistical Analysis Plan

Version History Log

Version	Date	Changes
0.1	28/04/2020	
0.2	29/04/2020	Minor edits
0.3	01/05/2020	Added details on the nature & analyses of outcomes
0.4	26/10/2020	Modified to account for historical controls
0.5	05/11/2020	Minor edits
0.6	16/11/2020	Added NEWS 2 score
1.0	18/11/2020	Minor edits

Contents

1.	Study Summary	3
2.	Introduction	4
2.1	Purpose and scope of the statistical analysis plan	5
2.2	Analysis organisation	5
2.3	Data checking	5
3	Trial Objectives (from Protocol).....	5
3.1	Primary objectives	5
3.2	Secondary objectives	5
3.3	Exploratory objective	6
4	Trial Design.....	6
4.1	Sample size calculation.....	6
4.2	Randomization	7
5	Data collection	7
5.1	Primary outcome measures	7
5.2	Secondary outcome measures	7
5.3	Exploratory endpoints.....	8
5.5	Duration of the intervention period and frequency of follow up.....	8
6	Data analysis plan	8
6.1	General statistical considerations.....	8
6.2	Summary of baseline characteristics.....	8
6.3	Analysis of primary outcome	9
6.4	Analysis of secondary outcomes.....	10
6.5	Sensitivity analysis.....	Error! Bookmark not defined.
6.6	Model checking.....	Error! Bookmark not defined.
7	Software	10
8	References	10
	Appendix – Schedule of assessment.....	11

1. Study Summary

For full details see the protocol (version 7.0, 30/10/2020).

Title	A pilot, open label, phase II clinical trial of nebulised recombinant tissue-Plasminogen Activator (rt-PA) in patients with COVID-19 ARDS: The Plasminogen Activator COVID- 19 ARDS (PACA) trial.
Short title	Nebulised rt-PA for ARDS due to COVID-19 – The PACA trial
Chief Investigator	[name]
Statisticians	[name] & [name]
Health economist	...
Design	Phase II, open label, multi-centre, pilot interventional study.
Primary objectives	
 1. Efficacy: Investigate the potential for efficacy of nebulised rtPA in patients presenting with severe COVID-19 requiring IMV or Non-invasive support with NIV OR continuous positive airway pressure (CPAP) OR high flow oxygen OR standard oxygen therapy. 2. Safety: Evaluate the safety of nebulised rtPA treatment.

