Primary Outcomes	
Efficacy
 
 1. Change in $\text{PaO}_2/\text{FiO}_2$ ratio from baseline (defined as 3 days prior to treatment), daily during treatment, end of treatment and 3 and 5 days post treatment in the groups receiving rtPA 
Safety
 
 1. Incidence and severity of major bleeding events directly attributable to the study drug 2. Decrease in fibrinogen levels to $< 1.5 \text{ gm/L}$ during treatment period and 48 hrs after the last dose of treatment 3. Number and nature of serious adverse events causally related to the treatment
Population	
Inclusion criteria
 
 1. Patients with COVID-19 confirmed by PCR 2. ≥ 16 years 3. Willing and able to provide written informed consent or where patient doesn't have capacity, consent obtained from a legal representative 4. Patients on IMV must meet both the following criteria: 
 a. $\text{PaO}_2/\text{FiO}_2 \leq 300$ b. Intubated > 6 hrs 5. Patients on NIV must meet all the following criteria: 
 a. $\text{PaO}_2/\text{FiO}_2 \leq 300$ or equivalent imputed by non-linear calculation from $\text{SpO}_2/\text{FiO}_2$ b. In-patient > 6 hours and being actively treated

	
c. On support with non-invasive ventilation OR continuous positive airway pressure (CPAP) OR high flow OR standard oxygen therapy.
 
Exclusion criteria
 
 1. Females who are pregnant 2. Concurrent involvement in another experimental investigational medicinal product 3. Known allergies to the IMP or excipients of IMP 4. A pre-existing bleeding disorder (e.g. severe haemophilia) 5. Pre-existing severe cardiopulmonary disease (e.g. incurable lung cancer, severe chronic obstructive lung disease, cardiomyopathy, heart failure or impaired contractility <estimated 40% LVEF or RVEF) 6. Fibrinogen < 2.0 g/L at time of screening 7. Patients considered inappropriate for critical care (prior decision re ceiling of care established) 8. Patients with active bleeding in the preceding 7 days 9. Patients who in the opinion of the investigator are not suitable.
Sample size	36: 12 participants receiving rtPA + standard of care (SOC), and 24 matched historical controls receiving SOC only.
Randomisation	Not applicable – study is open label.
Sponsor protocol number	132151
Funder (s):	Royal Free Charity
EudraCT No	2020-001640-26

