5.1 Primary outcome measures

Efficacy

- PaO₂/FiO₂ measured at multiple timepoints over the study period: baseline, during treatment, end of treatment, 3 days post end of treatment and 5 days post end of treatment.

Safety

- Incidence and severity of major bleeding events;
- Decrease in fibrinogen levels to < 1.5 gm/L during treatment period and 48 hrs after the last dose of treatment;
- Number and nature of serious adverse events causally related to the treatment.

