6.3 Analysis of primary outcome

The primary outcome for efficacy is oxygenation, measured using the PaO₂/FiO₂ ratio over time. The distributions of the primary outcomes will be summarised, by group, over time. Change in PaO₂/FiO₂ ratio from baseline will be checked visually using means & SE plots. If necessary, appropriate transformations of the data will be performed (e.g., using the natural logarithm).

Subject to the final sample size and data quality, PaO₂/FiO₂ ratio will also be compared between the SOC group (historical controls) and rtPA group using appropriate regression modelling, controlling for baseline oxygenation ratio:

$$OXY_i = \beta_0 + \beta_1 \cdot T_i + \beta_2 \cdot OXY0_i + \varepsilon_i,$$

where the i subscript denotes the i^{th} patient and

- OXY_i = PaO₂/FiO₂ ratio (oxygenation) at the end of treatment;
- T_i = group indicator (= 1 if patient is in the rtPA group, = 0 otherwise);
- $OXY0_i$ = PaO₂/FiO₂ ratio (oxygenation) at baseline;
- $\varepsilon_i \sim N(0, \sigma^2)$ = Normally distributed error term.

The estimate of the parameter β_1 and associated 95% confidence interval shall be reported, as well as a p-value pertaining to the hypothesis test of

$$H_0: \beta_1 = 0 \text{ versus } H_1: \beta_1 \neq 0.$$

Similarly, the use of models using oxygenation at other meaningful timepoints as outcome measure will be evaluated. Owing to a limited sample size, models shall not adjust for other baseline characteristics. Fitted models shall be checked, where appropriate, to ensure that modelling assumptions have been satisfied. Appropriate transformations of outcomes or other suitable approaches (e.g., robust or non-parametric methods) shall be explored if model assumptions are not satisfied.

For treatment safety, the incidence and severity (either major or minor) of bleeding events will be summarised with frequencies and percentages in each group. Fibrinogen levels will also be summarised graphically using plots of the mean, by group, over time. Finally, the number and nature of serious adverse events (SAEs) will be summarised. These events are defined in section 8 of the protocol.

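### The primary fibrinogen safety endpoint is set below 1.0 g/L in the protocol and below 1.5 g/L in the SAP, and protocol 7.10 disagrees with 2.6, 7.3.3 and 7.4 on the level for stopping dosing in one patient

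*SAP*

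**What the plan says.** **Endpoint.** SAP 5.1 defines the fibrinogen outcome as "Decrease in fibrinogen levels to < 1.5 gm/L during treatment period and 48 hrs after the last dose of treatment". The primary outcomes in the SAP study summary use the same level. The primary endpoints in the protocol summary set it at below "1.0 gm/L during treatment period and 48 hrs after the last dose of treatment", and protocol 10.1.2 agrees. Neither protocol passage restricts the level to one cohort. The SAP states that it was written against protocol version 7.0; the protocol supplied is version 10.0. Protocol 10.6 provides for a separate SAP for cohort 2, so the supplied SAP covers cohort 1.

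**Planned outputs.** For fibrinogen, SAP 6.3 says: "Fibrinogen levels will also be summarised graphically using plots of the mean, by group, over time". Protocol 10.6.2 says that "the change in fibrinogen levels will also be summarised at each post-baseline timepoint". Three general lines also bear on it. Protocol 10.6 provides for listings of the study data and says: "Continuous variables will be summarised using number of observations, mean, and standard deviation, median, inter-quartile range, minimum, and maximum values". It then says that categorical values are given as numbers and percentages. SAP 6.3 says that the distributions of the primary outcomes are summarised by group over time.

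**Stopping dosing in one patient.** Protocol 2.6, 7.3.3 and 7.4 each state that rtPA is stopped in a patient whose fibrinogen falls below 1.0 g/L. The cohort 1 bullet of protocol 7.10 explains its 50% reduction rule by referring to 1.5 g/L as the level already stated for stopping dosing in an individual.

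**The concern.** One primary safety endpoint has two definitions in the current documents, and nothing says which governs. The final analysis of cohort 1 was still awaited when protocol v10.0 was written (section 2.5), and the cohort 2 SAP is a separate document. Each could take its level from a different source, and the two cohorts could then report differently defined events under one name.

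The endpoint is also a yes-or-no event per patient within a dosing window, whereas the outputs specific to fibrinogen are group means and changes by timepoint. Protocol 2.6 treats plasma fibrinogen as the predictor of bleeding risk, and the DMC advises on moving to an RCT partly on safety data (12.2). How many patients met the endpoint is thus a figure that readers will look for.

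The 7.10 wording is a different matter, of clinical management rather than analysis. A reader of 7.10 is told that a level is stated elsewhere as a reason to stop dosing, and the sections that set that rule state another.

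**Working it through.** **Step 1. Endpoint definitions side by side.**

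| Place | Level | Cohort limit |
|---|---|---|
| Protocol summary, primary endpoints | below 1.0 g/L | none |
| Protocol 10.1.2 | below 1.0 g/L | none |
| SAP study summary | below 1.5 g/L | SAP covers cohort 1 |
| SAP 5.1 | below 1.5 g/L | SAP covers cohort 1 |

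The window is the same in all four: the treatment period and the 48 hours after the last dose.

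**Step 2. Which patients are classified differently.** Let m be a treated patient's lowest value in the window.
- m of 1.5 g/L or more: not an event under either definition.
- m from 1.0 to below 1.5 g/L: an event under the SAP, not under the protocol.
- m below 1.0 g/L: an event under both.

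**Step 3. Cohort 1 as known.** Protocol 4.1 gives 9 treated patients (6 on IMV and 3 on non-invasive support). Protocol 2.7.3 reports, as preliminary data, that none fell below 1.5 g/L. A value below 1.0 is also below 1.5, so 0/9 at the higher level implies 0/9 at the lower. The counts are 0/9 and 0/9, a difference of 0.

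**Step 4. Can the planned fibrinogen outputs show the event?** The documents give no distribution of fibrinogen values. Assume for illustration that the other patients average 3 to 5 g/L and that one patient is at 0.9 g/L. The group mean is (0.9 + (n − 1) × average) / n.
- n = 9: (0.9 + 8 × 3)/9 = 24.9/9 = 2.77, up to (0.9 + 8 × 5)/9 = 40.9/9 = 4.54 g/L.
- n = 6: (0.9 + 5 × 3)/6 = 15.9/6 = 2.65, up to (0.9 + 5 × 5)/6 = 25.9/6 = 4.32 g/L.

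Under this assumption every mean lies above both levels, so a mean plot would not reveal the event. The listings and the minimum values in protocol 10.6 would let a low value be found. A reader could also treat the endpoint as a categorical value (protocol 10.6) or as one of the primary outcomes whose distribution is summarised (SAP 6.3). Neither line names the level, the window or a patient count. For bleeding, by contrast, SAP 6.3 asks for frequencies and percentages outright.

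**Step 5. Individual dosing-stop level side by side.**

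| Place | Level | Cohort limit |
|---|---|---|
| Protocol 2.6 | below 1.0 g/L | none |
| Protocol 7.3.3 | below 1.0 g/L | none |
| Protocol 7.4 | below 1.0 g/L | none |
| Protocol 7.10 | 1.5 g/L, referred to as stated elsewhere | within the cohort 1 bullet |

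The cross-reference in 7.10 does not match any of the three sections that set the rule.

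**The case against.** The best case on the other side is that this is a difference of version and cohort. The SAP is tied to protocol 7.0 and knows nothing of cohort 2. Cohort 1 was already closed to recruitment. Several cohort 1 texts carry 1.5 g/L (the SAP, protocol 2.7.3 and the cohort 1 bullet of 7.10), and the entry limits also differ by cohort (2.0 g/L in 6.1.2, 1.5 g/L in 6.1.4). A cohort-specific level that was never labelled is therefore plausible. This stands as an explanation. It does not remove the mismatch, because 10.1.2, 7.3.3 and 7.4 carry no cohort limit and no passage assigns either level to one cohort. Version 7.0 was not supplied, so nothing can be said about whether the SAP matched it.

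A second objection is that the general lines on categorical values and on distributions of the primary outcomes already provide for a count. That stands in part: they could cover it. The fair statement is that no passage names the count explicitly, not that the plan rules it out or would leave a low value undetected.

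A third is that the 7.10 wording is explanatory text inside a rule about the first two cohort 1 patients, while the sections that set the individual rule agree with each other. That limits its weight; the wording still contradicts those sections.

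A reader might also infer that the SAP level would make any fall an event for a cohort 2 patient who enters at 1.5 g/L. The documents do not support this. The only endpoint supplied for cohort 2 is the protocol's, below 1.0 g/L, and nothing says that the SAP level will be carried over.

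**Conclusion.** The point holds as a contradiction between current texts that should be fixed. One primary safety endpoint has two levels over one window, and patients whose lowest value is from 1.0 to below 1.5 g/L are classified differently. The individual dosing-stop level in protocol 7.10 also disagrees with 2.6, 7.3.3 and 7.4.

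The size is small on present evidence. The preliminary cohort 1 count is 0/9 under both definitions, so no known result changes. This rests on the statement in protocol 2.7.3, which is marked as preliminary. The exposure is the definition used in the final cohort 1 report and in the cohort 2 SAP, together with an ambiguous safety text.

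A reader might infer that cohort 1 safety has been misreported, or that a patient was managed under the wrong level. The documents support neither: none of the nine was reported in the range where the levels differ. Confidence limits around 0/9 would not measure the problem either, because they are identical under both definitions and reflect only the small sample. The analysis is descriptive and the sample size has no statistical basis, so no error rate or power is affected.

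**What to change.** 1. Reconcile the SAP summary and 5.1 with the protocol summary and 10.1.2. If the level is meant to differ by cohort, say so in each place.
2. Reconcile the wording of protocol 7.10 with 2.6, 7.3.3 and 7.4. The levels are for the investigators and the DMC to settle; this review does not favour either.
3. In SAP 6.3 and in the cohort 2 SAP, name the number and percentage of rtPA-treated patients meeting the agreed definition from first dose to 48 hours after the last dose. Limit this to the treated groups (1, 2, 5 and 6), because the window depends on doses that the historical controls did not receive.

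Counts at a second level, and a listing of each patient's lowest value, are optional.

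The cost is wording in both documents and one row in a safety table. Fibrinogen is already among the local blood tests (protocol 7.6.2), so no new data are needed. SAP 2.1 already allows amendments that are documented and justified.

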5.2 Secondary outcome measures

- Changes in lung compliance (defined as tidal volume / (peak inspiratory pressure - PEEP)) from baseline and absolute values at day 5 (96 hrs \pm 2 hrs) and day 7 (144 hrs \pm 4hrs);
- Clinical status as assessed by a 7-point WHO ordinal scale at baseline and daily up to 5 days post end of treatment and at day 28, discharge or death (whichever comes first);
- Mean daily Sequential Organ Failure Assessment (SOFA) score at baseline through up to 5 days post end of treatment;
- Mean daily NEWS 2 score at baseline through up to 5 days post end of treatment, for NIV patients only;
- In follow up period, number of oxygenation free days, ventilator free days, intensive care stay, up to 28 days or death or discharge, whichever occurs first;

- Incidence and number of days of new oxygen use, non-invasive ventilation or high flow oxygen devices in the first 28 days;
- Incidence and duration of new mechanical ventilation use during in the first 28 days;
- In hospital mortality;
- Length of ICU stay post treatment;
- Length of ventilation;
- Use of vasopressors.

Further details on the outcomes, including a list of references, can be seen in the protocol.

5.3 Exploratory endpoints

Change in levels of plasma biomarkers of pro- and anti-inflammatory markers (interleukin-6, interleukin-8, interleukin-10 and interleukin-1Ra), endothelial injury (plasma von Willebrand factor) coagulation (procoagulants, anticoagulants, and fibrinolytic pathway) measure of tissue damage. Historical controls will not provide data for exploratory endpoints.

